4.1 Inclusion Criteria

- i) Ages 18 and over
- ii) Subjects capable of giving informed consent, or have an acceptable surrogate capable of giving consent on the subject's behalf
- iii) Planned peroral endoscopic myotomy

4.2 Exclusion Criteria

- i) cannot give consent
- ii) patients who are clinically unstable and/or require urgent/emergent intervention
- iii) previous esophageal myotomy
- iv) preexisting hypermagnesemia
- v) end-stage renal disease
- vi) neuromuscular disease, including but not limited to Guillain-Barre syndrome, myasthenia gravis, congenital myopathy, and muscular dystrophy
- vii) preexisting heart failure
- viii) severe ventricular systolic dysfunction (left or right ventricle)

4.3 Subject Recruitment and Screening

No patient health information will be collected prior to enrollment. When possible, the primary endoscopist/surgeon or other health care provider(e.g. nurse practitioner, nursing staff) will inform eligible participants of the study. If the patient expresses interest they will be approached by research study personnel. If they decline they will not receive any further information about the study. In cases where it is not feasible for an endoscopist to inform the patients of the study, or the patient has not yet met the endoscopist, a research personnel will screen for eligibility using chart review. Eligible patients will be approached about the study if history review reveals a potential candidate for the study. If the family expresses interest, the research personnel will proceed with consent and protocol. If patient decline interest, we will respect their decision and will not pursue the family any further for this study. Participants will be asked if they are participating in other studies. They will be allowed to participate in more than one study if it can be determined that this poses no increased risk to the participants or the integrity of the data collected for either study.

4.4 Early Withdrawal of Subjects

4.4.1 When and How to Withdraw Subjects

Patients will be informed that they may withdraw from the study at any time, for any reason, with no consequences for withdrawing, and the standard clinical care and procedures will continue as normal.

CONFIDENTIAL

This document is confidential and the property of Stanford University School of Medicine.

4.4.2 Data Collection and Follow-up for Withdrawn Subjects

All data will be de-identified and stored in Stanford-secured encrypted devices, only accessible to research personnel. For withdrawn subjects, we will attempt to seek permission for magnesium levels drawn during the defined follow-up period (postoperative days 0 and 1). This is related to the safety profile of the study drug. Otherwise, all other data related to the withdrawn subject will be destroyed, and no further follow-up information will be collected.

5 Study Drug

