7.2 Statistical Methods

Data will be expressed as means \pm SD, number (proportion), relative risk, 95% CI, absolute risk reduction, or number needed to treat.

The primary outcome is the incidence of esophageal spasm-related pain at 0 h postoperatively, compared using the chi-square test.

The secondary outcomes of the incidence of esophageal spasm-related pain at 24 hours postoperatively, intraoperative opioid usage, postoperative opioid consumption, and discharge opioid prescription will be compared using the chi-square test or Fisher's exact test as appropriate. Continuous variables will be compared using the Mann–Whitney *U* test. Categorical variables will be compared using the chi-square test or Fisher's exact test as appropriate.

Post hoc subgroup analyses will be conducted regarding the incidence of esophageal spasm-related pain according to achalasia type (e.g. type 1, 2, or 3), preoperative H2-receptor antagonist use, preoperative proton pump inhibitor use, and intraoperative opioid usage. *Post hoc* subgroup analysis will be further conducted on postoperative magnesium levels and the incidence of esophageal spasm-related pain at 24 hours.

All *P* values will be two-sided, and a value of $P < 0.05$ will be considered statistically significant.

Comparisons of postoperative pain between the two groups at time 0 h and time 24 h will be analyzed using the Mann–Whitney *U* test and performed using an adjusted significance level of 0.0125 (0.05/4) after *post hoc* analysis using the Bonferroni method.

Statistical analyses will be performed using R version 4.0.3.

CONFIDENTIAL

This document is confidential and the property of Stanford University School of Medicine.

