7.3 Subject Population(s) for Analysis

Enrollment will cease when the target sample size is obtained. Analyses will be performed on an intention-to-treat basis. All patients who are enrolled and randomly allocated for treatment will be included in the analysis.

8 Safety and Adverse Events

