8.1 Definitions

Adverse Event

An **adverse event** (AE) is any symptom, sign, illness or experience that develops or worsens in severity during the course of the study. Intercurrent illnesses or injuries should be regarded as adverse events. Abnormal results of diagnostic procedures are considered to be adverse events if the abnormality:

- results in study withdrawal
- is associated with a serious adverse event
- is associated with clinical signs or symptoms
- leads to additional treatment or to further diagnostic tests
- is considered by the investigator to be of clinical significance

Serious Adverse Event

Adverse events are classified as serious or non-serious. A **serious adverse event** is any AE that is:

- fatal
- life-threatening
- requires or prolongs hospital stay
- results in persistent or significant disability or incapacity
- a congenital anomaly or birth defect
- an important medical event

Important medical events are those that may not be immediately life threatening, but are clearly of major clinical significance. They may jeopardize the subject, and may require intervention to prevent one of the other serious outcomes noted above. For example, drug overdose or abuse, a seizure that did not result in in-patient hospitalization, or intensive treatment of bronchospasm in an emergency department would typically be considered serious.

All adverse events that do not meet any of the criteria for serious should be regarded as **non-serious adverse events**.

Adverse Event Reporting Period

The study period during which adverse events must be reported is normally defined as the period from the initiation of any study procedures to the end of the study treatment follow-up. For this study, the study treatment follow-up is defined as 30 days following the last administration of study treatment.

Preexisting Condition

CONFIDENTIAL

This document is confidential and the property of Stanford University School of Medicine.

A preexisting condition is one that is present at the start of the study. A preexisting condition should be recorded as an adverse event if the frequency, intensity, or the character of the condition worsens during the study period.

General Physical Examination Findings

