9.1 Confidentiality

Information about study subjects will be kept confidential and managed according to the requirements of the Health Insurance Portability and Accountability Act of 1996 (HIPAA). Those regulations require a signed subject authorization informing the subject of the following:

- What protected health information (PHI) will be collected from subjects in this study
- Who will have access to that information and why

CONFIDENTIAL

This document is confidential and the property of Stanford University School of Medicine.

- Who will use or disclose that information
- The rights of a research subject to revoke their authorization for use of their PHI.

In the event that a subject revokes authorization to collect or use PHI, the investigator, by regulation, retains the ability to use all information collected prior to the revocation of subject authorization. For subjects that have revoked authorization to collect or use PHI, attempts should be made to obtain permission to collect at least vital status (i.e. that the subject is alive) at the end of their scheduled study period.

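### Section 4.4.2 orders a withdrawn patient's collected data destroyed, so a recorded 0 h primary outcome can be erased despite the intention-to-treat rule in 7.3

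*Combined protocol and SAP*

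**What the plan says.** Section 4.4.1 tells patients that "they may withdraw from the study at any time, for any reason". Section 4.4.2 then covers the data of those who do. Permission will be sought for "magnesium levels drawn during the defined follow-up period (postoperative days 0 and 1"), on safety grounds. For everything else the rule is: "Otherwise, all other data related to the withdrawn subject will be destroyed, and no further follow-up information will be collected".

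Other sections bear on this:

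- **7.2:** "The primary outcome is the incidence of esophageal spasm-related pain at 0 h postoperatively", compared by chi-square test.
- **7.3:** analysis is by intention to treat, and "All patients who are enrolled and randomly allocated for treatment will be included in the analysis".
- **9.1:** if a subject revokes authorisation to use health information, the investigator "retains the ability to use all information collected prior to the revocation of subject authorization", and "attempts should be made to obtain permission to collect at least vital status".
- **8.1:** "For this study, the study treatment follow-up is defined as 30 days following the last administration of study treatment". Sections 8.1 and 8.2 also require adverse events to be recorded and followed to an end point.

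**The concern.** Stopping new data collection when a patient withdraws is defensible. Destroying what is already held is a different act, and 4.4.2 orders both.

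The primary outcome is fixed at 0 h, while participation runs to the morning of postoperative day 1 (6.4.1). Between the two, a patient can withdraw with the primary outcome already on file. Following 4.4.2 then removes that patient from the primary comparison after the result is known. If late withdrawal is related to pain or side effects and differs by arm, the comparison is biased. No later analysis can recover an outcome that has been destroyed.

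The same sentence would erase non-serious adverse events already recorded for that patient, although 8.2 requires all adverse events in the study period to be recorded.

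**Working it through.** **1. Does the rule reach randomised patients with a recorded outcome?**

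- Withdrawal has no time limit (4.4.1).
- The exception in 4.4.2 concerns levels from postoperative days 0 and 1, so the section contemplates patients who have been randomised and dosed.
- Only data already held can be destroyed, so the clause is more than a stop on collection.
- The 0 h assessment comes before the day 1 assessment (6.3, 6.4.1, 7.2), so there is a window for withdrawal after the outcome is recorded.
- No section exempts the 0 h outcome, and 7.3 does not say how a patient without one is included.

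Sections 4.4.2 and 7.3 therefore cannot both be followed for such a patient.

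**2. Inputs for the size of the effect**

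- From 7.1: 60% incidence; 45 per group raised to 50 for 10% dropout (45 / 0.90 = 50, which reproduces); two-sided 0.05.
- Assumed: k = 1, 2 or 5 patients deleted per affected arm. The plan gives no rate of late withdrawal. The upper value equals the whole dropout allowance, 0.10 × 50 = 5, although 7.1 does not define dropout.
- Assumed: chi-square without continuity correction, and no true effect (60% in both arms).

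**3. Method**

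With a of n control and b of m magnesium patients in pain after deletion, and p = (a + b)/(n + m):

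z = (a/n − b/m) / √[p(1 − p)(1/n + 1/m)]

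The false-positive rate is the total probability, over all pairs of Binomial(50, 0.60) counts, of those pairs giving |z| > 1.96 after deletion.

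**4. False-positive rate (5.2% with no deletion)**

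| Deletion pattern | k = 1 | k = 2 | k = 5 |
|---|---|---|---|
| Unrelated to outcome, both arms | 5.0% | 5.0% | 4.9% |
| Patients with pain, both arms | 5.2% | 5.3% | 5.5% |
| Patients with pain, magnesium arm only | 5.0% | 5.8% | 7.4% |
| Opposite patterns (extreme bound) | 5.8% | 7.6% | 20.6% |

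The last row deletes magnesium patients with pain and control patients without pain. The small dip at k = 1 in the third row reflects the discreteness of the counts.

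**5. Shift in the risk difference at expected counts (30/50 in each arm before deletion)**

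- Magnesium only: 30/50 − 29/49 = 0.8 points; 30/50 − 28/48 = 1.7; 30/50 − 25/45 = 4.4.
- Opposite patterns: 30/49 − 29/49 = 2.0 points; 30/48 − 28/48 = 4.2; 30/45 − 25/45 = 11.1.
- Pain-driven equally in both arms: 0 points.

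**6. Borderline results (illustrative counts, control first)**

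- 30/50 vs 20/50: p = 0.50, standard error √(0.25 × 0.04) = 0.10, z = 0.20/0.10 = 2.0, P = 0.046. Deleting one control patient with pain gives 29/49 vs 20/50, P = 0.056.
- 30/50 vs 21/50: P = 0.072. Deleting two magnesium patients with pain gives 30/50 vs 19/48, P = 0.043.

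**7. Power**

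The same enumeration for 60% vs 30% gives 87.6% at 50 per arm and 81.8% at 45. If the reduction in 7.1 is absolute, loss of numbers is covered and power is not the issue.

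**The case against.** The strongest reply is that the exposure is small. Participation lasts 2 days (3.1), and the window runs only from the recovery-unit assessment to the next morning. Patients are blinded (5.8), so withdrawal that differs by arm is not very likely. Reaching 7.4% takes five late withdrawals, all in the magnesium arm and all with pain. The 20.6% figure needs opposite patterns in the two arms, which nothing in the documents suggests. This stands: the expected shift is small, and the 20.6% is only a bound.

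Second, 7.3 has no rule for any missing 0 h outcome, so that gap exists without 4.4.2. True, but an outcome that was never observed differs from one that was observed and then destroyed.

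Third, allocation might be recovered from the numbered envelopes (5.3) or the electronic anesthetic record (5.9.4), which would allow a best/worst-case analysis. This helps in part, but the plan does not say that those records may be used after withdrawal, and they do not restore the outcome. Hospital records and serious adverse event forms already filed (8.3.1) would also survive.

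Fourth, 9.1 permits use of earlier data and does not require it, so it is not a strict contradiction. That is fair. It does show that the protocol itself sees no need for destruction when authorisation is revoked.

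Fifth, on follow-up, 8.1 already provides for notifying the sponsor of related events after a subject discontinues. This partly eases the conflict with the 30-day reporting period, which is secondary here.

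**Conclusion.** The concern holds. As written, 4.4.2 can erase a recorded primary outcome that 7.3 requires in the analysis, and it would also erase recorded non-serious adverse events.

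Under the stated assumptions, deletion that is random or similar in both arms leaves the false-positive rate near 5%. One-sided deletion of 1 to 5 magnesium patients with pain gives 5.0% to 7.4%, with a shift of 0.8 to 4.4 points. Patients who stay in the study, or who withdraw before 0 h, lose no recorded primary outcome.

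The point must be fixed because the loss is irreversible and defeats the plan's own analysis population, not because a large shift is expected. In a borderline result, one or two deletions are enough to change the conclusion.

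**What to change.** Replace the destruction sentence in 4.4.2 with wording such as:

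> Data collected up to withdrawal, including allocation, treatment received, the 0 h outcome and adverse events, are retained and analysed in the assigned arm. After withdrawal no new data are actively collected without the patient's permission, which will be sought for magnesium levels and adverse event follow-up. Safety information already held or volunteered is still reported under section 8.

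Align the consent form with this text. In 7.3, commit to reporting the number of patients without a 0 h outcome by arm; a best/worst-case sensitivity analysis is optional.

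The cost is protocol and consent wording, with no extra patients or procedures. The change needs to be in place before any late withdrawal occurs. The consent form is not among the documents reviewed, so for patients already enrolled, retention depends on what their form promised.

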At screening, any clinically significant abnormality should be recorded as a preexisting condition. At the end of the study, any new clinically significant findings/abnormalities that meet the definition of an adverse event must also be recorded and documented as an adverse event.

Post-study Adverse Event

All unresolved adverse events should be followed by the investigator until the events are resolved, the subject is lost to follow-up, or the adverse event is otherwise explained. At the last scheduled visit, the investigator should instruct each subject to report any subsequent event(s) that the subject, or the subject's personal physician, believes might reasonably be related to participation in this study. The investigator should notify the study sponsor of any death or adverse event occurring at any time after a subject has discontinued or terminated study participation that may reasonably be related to this study. The sponsor should also be notified if the investigator should become aware of the development of cancer or of a congenital anomaly in a subsequently conceived offspring of a subject that has participated in this study.

Abnormal Laboratory Values

A clinical laboratory abnormality should be documented as an adverse event if any one of the following conditions is met:

- The laboratory abnormality is not otherwise refuted by a repeat test to confirm the abnormality
- The abnormality suggests a disease and/or organ toxicity
- The abnormality is of a degree that requires active management; e.g. change of dose, discontinuation of the drug, more frequent follow-up assessments, further diagnostic investigation, etc.

Hospitalization, Prolonged Hospitalization or Surgery

Any adverse event that results in hospitalization or prolonged hospitalization should be documented and reported as a serious adverse event unless specifically instructed otherwise in this protocol. Any condition responsible for surgery should be documented as an adverse event if the condition meets the criteria for an adverse event.

Neither the condition, hospitalization, prolonged hospitalization, nor surgery are reported as an adverse event in the following circumstances:

- Hospitalization or prolonged hospitalization for diagnostic or elective surgical procedures for a preexisting condition. Surgery should **not** be reported as an outcome of an adverse event if the purpose of the surgery was elective or diagnostic and the outcome was uneventful.

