8.2 Recording of Adverse Events

At each contact with the subject, the investigator must seek information on adverse events by specific questioning and, as appropriate, by examination. Information on all adverse events should be recorded immediately in the source document, and also in the appropriate adverse event module of the case report form (CRF). All clearly related signs, symptoms, and abnormal diagnostic procedures results should be recorded in the source document, though should be grouped under one diagnosis.

All adverse events occurring during the study period must be recorded. The clinical course of each event should be followed until resolution, stabilization, or until it has been determined that the study treatment or participation is not the cause. Serious adverse events that are still ongoing at the end of the study period must be followed up to determine the final outcome. Any serious adverse event that occurs after the study period and is considered to be possibly related to the study treatment or study participation should be recorded and reported immediately.

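### Section 4.4.2 destroys a withdrawn subject's data and ends follow-up, which contradicts the adverse event rules in 8.1 and 8.2 and fits badly with 9.1; the sections must be reconciled

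*Combined protocol and SAP*

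**What the plan says.** Section 4.4.2 makes one exception for a withdrawn subject: "we will attempt to seek permission for magnesium levels drawn during the defined follow-up period (postoperative days 0 and 1"). It explains this exception by the safety profile of the drug. For the rest, "all other data related to the withdrawn subject will be destroyed, and no further follow-up information will be collected". The closing words, "no further follow-up information will be collected", are not limited to efficacy data.

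Section 4.4.1 lets a subject withdraw at any time and for any reason, and says that "the standard clinical care and procedures will continue as normal".

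The safety sections are worded for all subjects:

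- Section 8.1 sets the adverse event reporting period to end 30 days after the last study treatment. It says that "All unresolved adverse events should be followed by the investigator until the events are resolved", with loss to follow-up or another explanation as the alternative end points. It also has the investigator tell the sponsor of any possibly related death or adverse event after a subject has discontinued.
- Section 8.2 makes recording of every adverse event in the study period mandatory, and adds: "Serious adverse events that are still ongoing at the end of the study period must be followed up to determine the final outcome".
- Section 9.1, for subjects who revoke authorization to use their health information, lets the investigator go on using what was collected beforehand and says that "attempts should be made to obtain permission to collect at least vital status".

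**The concern.** Section 4.4.2 does two separate things. It removes what has already been collected, and it stops new collection. Both touch adverse events. The first could delete events that 8.2 has just required the site to record. The second closes off the 30-day period, the follow-up of unresolved events and the outcome of ongoing SAEs. The protocol does not say that one section gives way to the other, so two members of the same study team could handle the same withdrawal in opposite ways and each point to the text.

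At stake is whether the safety record of a placebo-controlled drug trial with 50 patients per arm is complete. Section 8.1 itself foresees a link between events and withdrawal: an abnormal diagnostic result counts as an adverse event if, among other criteria, it "results in study withdrawal". Under 4.4.2 the record of such an event could be destroyed, and its follow-up ended, by the withdrawal that made it reportable. A magnesium level from postoperative day 0 or 1 does not show whether a clinical event occurred or how it ended.

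**Working it through.** **Step 1: the rules side by side.**

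| Question about a withdrawn subject | Section 4.4.2 | Other sections |
|---|---|---|
| Adverse events recorded before withdrawal | Destroyed | 8.2: must be recorded. 8.3.1: a copy of the SAE form stays on file at the site. 9.1: prior information may be used even after authorization is revoked |
| New events up to 30 days | Not collected | 8.1 and 8.2: within the reporting period, all recorded |
| Unresolved events | Not followed | 8.1: followed until resolved, lost to follow-up or otherwise explained |
| SAEs ongoing at the end of the study period | Not followed | 8.2: followed to final outcome |
| Related death or event after discontinuation | Not collected | 8.1: sponsor notified |
| Vital status | Not collected | 9.1: attempt to get permission, if authorization was revoked |
| Magnesium levels | Sought with permission | No conflict |

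None of the entries from 8.1 and 8.2 exempts withdrawn subjects, and the sponsor notification clause names discontinued subjects expressly. Rows 1 to 4 cannot be satisfied together with 4.4.2. Row 5 is a weaker conflict, because a site could pass on what it happens to learn. Row 6 applies only where the withdrawn subject also revokes authorization.

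**Step 2: which clause does what.** An event that happens before withdrawal is recorded at once under 8.2, so ending later follow-up would not remove it; only the destruction clause would. An event that starts or evolves after withdrawal is lost through the follow-up clause. A repair has to cover both.

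**Step 3: how many subjects.** The inputs are 45 per group and 10% dropout, from section 7.1. The plan's own figure reproduces: 45 / (1 − 0.10) = 50 per group. The allowance is therefore 50 − 45 = 5 per arm, or 10 of 100. The protocol does not say how many of these would be withdrawals, or withdrawals after dosing. The number of dosed magnesium patients affected, within that allowance, runs from 0 to 5.

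**Step 4: what losing 5 would mean, under stated assumptions.**

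- *Withdrawal unrelated to events.* With no events seen, the one-sided 95% upper bound on an event rate is 1 − 0.05^(1/n). It is 5.8% for n = 50 and 6.4% for n = 45. For an assumed true rate of 2%, the chance of seeing at least one event is 1 − 0.98^n: 64% for n = 50 and 60% for n = 45.
- *Extreme case.* All 5 were dosed with magnesium, had a recorded event and withdrew, and nobody else had one. The full record is 5/50 = 10% (Clopper-Pearson 95% interval 3.3% to 21.8%). After destruction it is 0/45, with a two-sided 95% upper limit of 1 − 0.025^(1/45) = 7.9%. This measures the destruction clause, not the follow-up clause.
- *No withdrawals after dosing.* No magnesium safety data are lost.

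**The case against.** The best defence is that 4.4.2 is a deliberate privacy choice and that less is lost than appears. SAEs reach the sponsor within 24 hours under 8.3.1, so those arising before withdrawal should already be known. The 8.1 duty to follow unresolved events has its own end points. The 8.2 sentence on ongoing SAEs speaks of the end of the study period, not of withdrawal. Participation is expected to last 2 days, safety is not an endpoint, and section 7 plans no adverse event comparison.

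Part of this stands: it lowers the likely practical loss and makes the sponsor notification clause a softer conflict. It does not remove the contradiction. Recording all adverse events cannot be combined with destroying all data but magnesium levels, and the 30-day period is stated without exception. Nor does privacy settle the matter, since 4.4.2 itself accepts seeking safety data with permission.

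Four stronger readings are tempting, and the documents do not support them:

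- *The patients lost are those most likely to have had a problem.* Withdrawal may precede dosing, occur on saline or have any reason. The 8.1 criterion cited above is one of five for abnormal diagnostic results and gives no rate.
- *Safety follow-up stops.* Standard care continues under 4.4.1. What stops is trial data collection, and that only if 4.4.2 is the rule applied, which the protocol leaves open.
- *Section 9.1 requires vital status for every withdrawn subject.* It covers revoked authorization only, and asks for attempts to get permission.
- *The trial will report 0/45 where the truth is 5/50.* This is an outer bound under assumptions the documents do not make, and no such rate is a planned output.

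**Conclusion.** The contradiction between 4.4.2 and sections 8.1 and 8.2 is real and should be resolved; the tension with 9.1 is secondary. As written, 4.4.2 permits the loss of recorded adverse events and of later trial safety information for withdrawn subjects, who may include dosed patients with an event. The size cannot be derived from the documents. Within the plan's dropout allowance it lies between none and 5 patients per arm. If withdrawal is unrelated to events, the effect on precision is small. If it is related, the effect could be larger and would depend on an association for which the protocol gives no figure. The conclusion on the wording does not rest on these numbers.

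**What to change.** Reconcile 4.4.2 with 8.1, 8.2 and 9.1 by replacing both the destruction clause and the follow-up clause. Changing only the second would leave recorded events exposed. Suggested content:

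- Safety data collected before withdrawal (adverse events, SAEs, magnesium levels) are retained and reported.
- After withdrawal, permission is sought to collect adverse events through the 30-day period, ongoing SAEs to outcome, and vital status, along with magnesium levels.
- If permission is refused, no new data are collected. Safety data already recorded, and the date and stated reason for withdrawal, are kept.
- Withdrawal from study procedures is recorded separately from withdrawal from all follow-up.

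The consent form should be aligned with this text. It was not among the pages available here, so what it now promises needs checking. The cost is a wording change in one section, the matching consent sentence, and a few follow-up contacts, made only with permission, for perhaps 10 patients at the planned dropout rate.
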